6.4.4 Reporting of serious adverse events

Investigators and other study site personnel must inform appropriate AstraZeneca representatives via the WBDC system of any SAE that occurs in the course of the study within 1 calendar day (ie, immediately but no later than the end of the next business day) of when he or she becomes aware of it. Follow-up information on SAEs must also be reported by the investigator with the same time frame.

The AstraZeneca representative will work with the investigator to compile all the necessary information and ensure that all the necessary information is provided to Bristol-Myers Squibb Global Pharmacovigilance and Epidemiology within one calendar day of initial receipt for fatal and life threatening events and within three calendar days of initial receipt for all other SAEs.

All SAEs have to be reported, whether or not considered causally related to the investigational product, or to the study procedure(s). All SAEs will be recorded in the eCRF. SAEs will be recorded from the time of informed consent.

The investigator and/or Sponsor are responsible for informing the Ethics Committee (EC) about the SAE as per local requirements. Reporting of SAEs to the Regulatory Authority is the responsibility of Bristol-Myers Squibb.

An automated email alert will be sent to the designated AstraZeneca representative, when the page with SAE information is saved in WBDC system by the Investigators or other site personnel. If the WBDC system is not available, then the Investigator or other study site personnel reports by fax an SAE to the appropriate AstraZeneca representative. A paper back-up SAE report is used for this purpose. The same reporting time frames still apply. The investigator is responsible for completing the eCRF as soon as the system becomes available again. The AstraZeneca representative will forward all information relevant to the SAE to Bristol-Myers Squibb Pharmacovigilance via fax or email.

6.4.5 Laboratory safety assessment

Blood and urine samples for determination of clinical chemistry, haematology and urinalysis will be taken at the times indicated in the Study Plan (see [Table 2](#)).

The following laboratory variables will be measured. For blood volume see Section [7.1](#)

Table 7 Safety laboratory variables

Visit	1	2	3	4	5	6	7	8	9	10	11	12	13	14
Study week	-12 or -6	-10	-7	-4	-1	0	1	4	8	12	16	20	24	27
Haematology														
Haemoglobin	X			X		X	X	X	X	X	X	X	X	X
Haematocrit	X			X		X	X	X	X	X	X	X	X	X
Red blood cell count	X			X		X	X	X	X	X	X	X	X	X
White blood cell count and differential	X			X		X	X	X	X	X	X	X	X	X
Platelet count	X			X		X	X	X	X	X	X	X	X	X
Clinical chemistry (serum)														
AST (SGOT)	X			X		X	X	X	X	X	X	X	X	X
ALT (SGPT)	X			X		X	X	X	X	X	X	X	X	X
Alkaline Phosphatase (ALP)	X			X		X	X	X	X	X	X	X	X	X
CK	X			X		X	X	X	X	X	X	X	X	X
TB	X			X		X	X	X	X	X	X	X	X	X
Blood Urea Nitrogen (BUN)	X			X		X	X	X	X	X	X	X	X	X
Electrolytes ^a	X			X		X	X	X	X	X	X	X	X	X
Total protein	X			X		X	X	X	X	X	X	X	X	X
Albumin	X			X		X	X	X	X	X	X	X	X	X
Uric acid	X			X		X	X	X	X	X	X	X	X	X
Serum Creatinine (SCr)	X			X		X	X	X	X	X	X	X	X	X
eGFR (Japanese guideline formula) ^b	X			X		X	X	X	X	X	X	X	X	X
Serum Cystatin C						X							X	
PTH						X							X	X
TSH	X													
PT	X													
PTT	X													
Hepatitis Screen Panel ^c	X													
Urinalysis (dipstick)														
Glucose ^d	X			X		X	X	X	X	X	X	X	X	X
Blood ^e	X			X		X	X	X	X	X	X	X	X	X
Pregnancy test ^f	X			X		X	X	X	X	X	X	X	X	X
Urinalysis (spot urine)														
Creatinine	X					X			X		X		X	
Albumin	X					X			X		X		X	
UACR	X					X			X		X		X	

Table 7 Safety laboratory variables

Visit	1	2	3	4	5	6	7	8	9	10	11	12	13	14
Study week	-12 or -6	-10	-7	-4	-1	0	1	4	8	12	16	20	24	27
Na	X					X			X	X	X		X	
Glucose ^d	X					X			X	X	X		X	

- a Electrolytes: Sodium, Bicarbonate, Potassium, Chloride, Calcium, Magnesium, Phosphorus
b The eGFR will be estimated by the abbreviated Japanese guideline formula and reported by central laboratory.
c Includes anti-HAV (IgM, IgG), HBsAg, anti-HBc (igG, IgM) and anti-HCV.
d Result will be blinded after Visit 6.
e Microscopy if dipstick positive for blood
f Urine HCG pregnancy test for WOCBP (HCG minimum sensitivity of 25 IU/L) (dipstick analyzed at the study centre)

6.4.6 Physical examination

- A brief physical examination should include the cardiovascular system, lungs, abdomen, and extremities, and any organ system pertinent to the subject’s signs, symptoms, or AEs. The subject should always be evaluated for the presence of oedema.
- A complete physical examination should include general appearance, head, eyes, ears, nose, throat, neck, cardiovascular system, lungs, abdomen, lymph nodes, extremities, neurological system, skin, and musculoskeletal system. The subject should always be evaluated for the presence of oedema.

Baseline data is collected at Visit 6, and new findings discovered on subsequent physical examinations should be recorded as changes from baseline.

6.4.7 ECG

Resting 12-lead ECG

A 12-lead ECG will be taken after the subject has been lying down resting. The ECG will be evaluated by the investigator and entered as ‘Normal’ or ‘Abnormal’ in the eCRF. If the ECG is evaluated as “Abnormal” the investigator should document the specific abnormality.

6.4.8 Vital signs

6.4.8.1 Pulse and blood pressure

One pulse measurement will be taken after the subject has been sitting and resting for at least 5 minutes and before blood samples are taken. The pulse measurement will be followed by three BP measurements separated by 2 minutes each. All three BP readings should be recorded. At Visit 1 the seated BP will be recorded three times in both the left and the right arms. All three measurements should be made in one arm before transferring the cuff to the other arm. The arm with the highest mean seated BP readings will be the one used for all subsequent readings throughout the study. BP readings should be taken while the subject is in a comfortable seated

position with the arm supported at the level of the heart. All readings should be recorded. Ideally, BP should be measured with the same machine, at the same time of day, and by the same personnel at each visit. A standard mercury sphygmomanometer with a standardised cuff adapted to the size of the subject's arm is recommended. Oscillometric devices (such as Dynamap) may be used at sites where:

- a mercury sphygmomanometer is not available, or
- a mercury sphygmomanometer is available, but site staff is not practiced in its use
- use of mercury devices is restricted by local law.

6.4.8.2 Orthostatic blood pressure

At selected visits where orthostatic BP and pulse are collected, supine and standing measurements should be made after the seated BP and pulse measurements have been made, using the same arm that was used for the seated BP measurements. All readings should be recorded. Ideally, BP should be measured with the same machine, at the same time of day, and by the same personnel at each visit.

Supine BP and pulse

The supine BP and pulse must be measured prior to the standing BP and pulse. After the subject rests in the supine position for at least 5 minutes, supine BP and pulse will be determined from three replicate measurements obtained at least 1 minute apart. All three readings must be recorded. For study analyses, the average of the three BP and pulse readings will be used.

Standing BP and pulse

After the supine BP and pulse measurements are obtained, the subject will stand for 2 to 3 minutes. After this time, the BP will be measured with the arm supported at the level of the heart. Standing BP and pulse will be determined from three replicate measurements obtained at least 1 minute apart. All 3 readings must be recorded. For study analyses, the average of the three BP and pulse readings will be used.

6.4.9 Other safety assessments

Self-monitored plasma glucose readings and hypoglycemic events will be collected in a subject diary and reviewed by the investigator at each visit.

6.4.9.1 Fasting plasma glucose concentrations and hypoglycemic events

Subject self-monitoring of FPG is performed in order to reduce the risks associated with prolonged hyperglycemia and to confirm symptoms of hypoglycemia. Subjects will be asked to perform self-monitoring of FPG using glucometers provided by AstraZeneca. The subjects will receive instructions for the use of the glucometer according to the manufacturer's instructions.

FPG should be self-monitored at least every second day between Visits 2 and 6 and at least once a week between Visits 6 and 8. The results should be recorded in the subject diary, which will be

collected and reviewed by the study personnel at each visit starting with Visit 3; a print out will be stored in the investigator study file.

The memory of the glucometer should be reviewed and compared with the readings in the subject's diary. The glucose values should be reviewed by the study personnel to identify any unusually high or low values, and to confirm that self-monitoring was performed by the subject. If fingerstick glucose values are discordant with central laboratory results or with clinical symptoms, the subject's glucometer should be tested and the glucometer instructions should be re-reviewed with the subject.

If self-monitored FPG is above 270 mg/dL (15 mmol/L) from Week - 4 (Visit 4) to Week 4 (Visit 8), and above 240 mg/dL (13.2 mmol/L) from Week 4 (Visit 8) to Week 24 (Visit 13), the subject should repeat the FPG on the same day. If the second FPG value is above 270 mg/dL (15 mmol/L), or 240 mg/dL (13.2 mmol/L), respectively, the subject should contact the study centre and be scheduled for a central laboratory FPG measurement within one week.

If central laboratory values show similar values, the subject should be discontinued.

A separate section in the eCRF will be used to document all reported episodes of hypoglycemia after Week - 4 (Visit 4). The subjects will be asked to check their blood glucose if they develop symptoms suggestive of hypoglycemia and to record specific symptoms in the subject diary. The Investigator is responsible for questioning the subject about all symptoms reported in the diary and for determining if they meet the clinical definition of hypoglycemia. Only symptoms and/or blood glucose values that meet the definition of hypoglycemia should be reported on the hypoglycemia eCRF pages.

A hypoglycemic event can be either:

- Symptoms of hypoglycemia with a low blood glucose reading (<63 mg/dL [<3.5 mmol/L])
- A low blood glucose reading (<63 mg/dL [<3.5 mmol/L])
- Symptoms of hypoglycemia without a blood glucose reading

Hypoglycemic episodes or discontinuation due to hypoglycemia should not be reported on the AE eCRF page unless the event fulfils protocol criteria for a SAE (See Section 6.4.2). In this case, an SAE must be reported in addition to the hypoglycemia eCRF pages for hypoglycemia.

Symptoms suggestive of hypoglycemia with an associated capillary or plasma glucose value ≥ 63 mg/dL (≥ 3.5 mmol/L), should be recorded as an AE rather than as a hypoglycemic event. If the physician does not consider the glucose measurement to be accurate, however, the event should be documented as a hypoglycemic event in the hypoglycemia eCRF.

For the evaluation of hypoglycemic events, this study will use the definitions provided in the CPMP guidance on clinical investigation of medicinal products in the treatment of diabetes mellitus, as described below.

- Major hypoglycemic events, defined as symptomatic events requiring external assistance due to severe impairment in consciousness or behaviour, with a capillary or plasma glucose value <54 mg/dL (<3.0 mmol/L), and prompt recovery after glucose or glucagon administration.
- Minor hypoglycemic event, defined as either a symptomatic episode with a capillary or plasma glucose measurement <63 mg/dL (<3.5 mmol/L) regardless of need for external assistance or an asymptomatic capillary or plasma glucose measurement below 63 mg/dL (3.5 mmol/L) , that does not qualify as a major episode
- Events suggestive of hypoglycemia, defined as a symptomatic event without a confirmatory blood glucose measurement.

Data to be collected for each hypoglycemic event:

- Date and time of episode (start and stop)
- Whether the subject was sleeping at the time of the event
- Whether symptoms were present, and list of symptoms
- Possible contributing factors
- Whether a fingerstick value was obtained, and if so, the plasma glucose value
- Whether intervention was needed for recovery
- How the episode was treated
- Whether recovery was prompt after treatment
- Time of last anti-diabetic agents administration
- Time of last meal and its contents

The subject diary will be reviewed and the hypoglycemic event data will be transcribed into the eCRFs at each clinical visit. A new diary for the next period will be handed over to the subject if needed. If a major hypoglycemic event or more than one minor event has occurred since the previous visit, the subject should contact the investigator.

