3.1.4.1 Rescue Treatment

Subjects with inadequate glycemic control based on glycemic criteria as outlined in Table 1 can remain in the study and can receive rescue therapy with metformin following Japanese local regulation and treatment guideline. In case of intolerability, contraindication or hypersensitivity to metformin or in case of eGFR < 60 ml/min, glymeperide can be used as rescue therapy. In case of inappropriateness of using both metformin and glymeperide, subjects will be withdrawn from this study. If glycemic control is not improved by the rescue therapy, the investigators can consider the discontinuation of the study after consulting with study delivery physician of AZKK.

During Visit 10 (Week 12) to Visit 13 (Week 24), if the results of FPG at the visit show more than 200 mg/dL twice in a row, the investigator consider to start rescue treatment.

Table 1 Criteria for initiation of rescue therapy during the randomised treatment period

Period	Central Laboratory FPG
From Visit 10 (Week 12) to Visit 13 (Week 24)	FPG >200 mg/dL (twice in a row ^a)

a During Visit 10 to 13, if the results of FPG at the visit show more than 200 mg/dL, the investigators should set up acting visit at some other day in order to recheck the FPG at central laboratory. If the results of FPG show more than 200 mg/dL consecutively at this second visit, the investigators can consider to start rescue treatment.

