5.6 Concomitant and post-study treatment(s)

Changes in concomitant medication should be avoided during study participation, with the exception of situations defined in this protocol, but medication, which is considered necessary for the subject’s safety and well-being, may be given at the discretion of the investigators, who must decide if the subject should remain in study or need to be dismissed from study due to subject’s safety or interference with study objectives.

The administration of all medication must be recorded in the appropriate sections of the electronic case report form (eCRF) with trade names, dosages, dates of starting and ending of medication and reason for therapy.

After having completed or discontinued the study, subjects will receive usual care and anti-diabetic agents according to the investigator's judgement and according to local medical practice.

Prohibited Therapies

- Weight loss medication, including but not limited to mazindol, sibutramine, phentermine, orlistat, rimonabant, benzphetamine, diethylpropion, methamphetamine, and/or phendimetrazine
- Antiviral drugs (delavirdine, indinavir, nelfinavir, ritonavir, saquinavir)

- Treatment with systemic glucocorticoids equivalent to oral prednisolone ≥ 10 mg (betametasone ≥ 1.2 mg, dexamethasone ≥ 1.5 mg, hydrocortisone ≥ 40 mg) per day (two temporary periods of higher daily doses for no longer than 7 days each are allowed).
- Anti-diabetic agents except for the study medication and rescue therapies (Anti-diabetic agents planned to be stopped for wash-out are allowed to be used until the beginning of wash-out period. After completion of the treatment period, alternative anti-diabetic treatment will be initiated according to standard medical practice.)

Restricted Therapies

- Insulin use is permitted in the following cases:
 - For up to 14 days total during the study and up to 7 continuous days if subjects are unable to take oral medications (for example during a gastrointestinal illness)
 - For up to 14 days total during the study and up to 7 continuous days if there is a documented illness or infection that requires additional therapy for maintaining glycemic control
 - For up to 14 days total during the study and up to 7 continuous days if subjects have to temporarily stop investigational product and rescue therapies due to requirements of this clinical study protocol.

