5.8.1 Criteria for discontinuation from the study

Subjects may be discontinued from study treatment and assessments at any time. Specific reasons for discontinuing a subject are:

General discontinuation criteria:

1. Voluntary discontinuation by the subject who is at any time free to discontinue his/her participation in the study, without prejudice to further treatment
2. Risk to subjects as judged by the investigator, AstraZeneca and/or Bristol-Myers Squibb
3. Severe non-compliance to protocol as judged by the investigator, AstraZeneca and/or Bristol-Myers Squibb
4. Incorrectly enrolled subjects (See Section 5.3)
5. Subject lost to follow-up defined by inability to reach the subject after 3 documented phone calls, faxes, or emails. All attempts at contact should be documented in the subject’s medical record.
6. AE, ie, any clinical AE, laboratory abnormality or intercurrent illness which, in the opinion of the investigator, indicates that continued participation in the study is not in the best interest of the subject

Study-specific discontinuation criteria:

7. Use of (need for) any anti-diabetic agents, except for rescue treatment, other than investigational product.
8. Treatment with systemic glucocorticoids equivalent to oral prednisolone ≥ 10 mg/day (two temporary periods of higher daily doses for no longer than 7 days each are allowed)
9. Major and/or frequent hypoglycemic events; If more than one event of severe hypoglycemia, defined as symptomatic events requiring external assistance due to severe impairment in consciousness or behaviour, with a capillary or plasma glucose value < 3 mmol/L (< 54 mg/dL), and prompt recovery after glucose or glucagon

administration occurs, or if the investigators decides that current treatment poses the subject at risk of either repeated hypoglycemic events or severe hypoglycemia.

10. Pregnancy confirmed by a positive pregnancy test or otherwise verified
11. Change in kidney function (see Appendix F for further guidance):
 - For subjects treated with metformin: For subjects with a central laboratory eGFR <60 mL/min or with an increase in SCr of ≥ 0.5 mg/dL (44.2 $\mu\text{mol/L}$) above the baseline value (Visit 6), an increase in SCr of ≥ 0.5 mg/dL above the baseline value (Visit 6) confirmed by a repeated measurement within one week or eGFR <60 mL/min
 - For subjects not treated with metformin: Subject with following criteria will be scheduled for an additional visit within one week.
 - (a) eGFR <45 ml/min

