- the proportion of subjects achieving a therapeutic glyceic response, defined as HbA1c $< 6.5\%$, at Week 24 (LOCF)
- the proportion of subjects achieving a therapeutic glyceic response, defined as HbA1c $< 7\%$ at Week 24 (LOCF) in subjects with baseline HbA1c $\geq 7\%$.
- the proportion of subjects discontinued for lack of efficacy or rescued for failing to maintain FPG below pre-specified rescue criteria at Week 12, 16, and 24 (LOCF)
- the proportion of subjects with baseline elevated BP (baseline SBP ≥ 130 mmHg and/or baseline DBP ≥ 80 mmHg) who achieve a seated BP of $< 130/80$ mmHg at Week 24 (LOCF)

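### In Weeks 12-24 a subject with confirmed high fasting glucose can meet both a discontinuation rule (6.4.9.1) and a stay-and-rescue rule (3.1.4.1), and nothing says which governs

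*Protocol*

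**What the plan says.** **Discontinuation rule (6.4.9.1).** When self-monitored FPG is "above 240 mg/dL (13.2 mmol/L) from Week 4 (Visit 8) to Week 24 (Visit 13), the subject should repeat the FPG on the same day". Should that repeat reading also exceed the limit, a central laboratory FPG follows within one week, and then: "If central laboratory values show similar values, the subject should be discontinued". No exception is made for Weeks 12-24 or for subjects eligible for rescue.

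**Rescue rule (3.1.4.1, Table 1).** From Visit 10 (Week 12) to Visit 13 (Week 24), a subject with central FPG above 200 mg/dL on two consecutive tests, the second on another day, "can remain in the study and can receive rescue therapy with metformin". There is no upper limit. If rescue does not help, discontinuation is something the investigator may consider after consulting the sponsor's physician.

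**Discontinuation list (5.8.1).** It contains no FPG threshold and no lack-of-efficacy item. Item 7 is "Use of (need for) any anti-diabetic agents, except for rescue treatment, other than investigational product".

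**Home-testing schedule (6.4.9.1).** At least every second day between Visits 2 and 6, then "at least once a week between Visits 6 and 8". No frequency is given after Visit 8.

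**Related outcome (12.2.2.3).** One secondary outcome combines subjects who stopped for lack of efficacy with those "rescued for failing to maintain FPG below pre-specified rescue criteria at Week 12, 16, and 24 (LOCF").

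**The concern.** Whether a subject with failing control leaves the trial or stays on blinded treatment with added rescue should not depend on which section a site happens to read. In Weeks 12-24 the two sections can give opposite answers for the same person. The same clash can arise after rescue has started: persistent values above 240 mg/dL lead to discontinuation under 6.4.9.1, but only to an option to discontinue under 3.1.4.1.

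Three things are at stake.

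- **Retention and safety exposure.** A discontinued subject has end-of-treatment procedures within 7 days and a follow-up visit three weeks after stopping (5.8.2). A rescued subject stays on treatment to Week 24.
- **Body weight, a key secondary endpoint in the testing hierarchy.** Section 12.2.2 excludes post-rescue values for glycaemic endpoints only, while 11.1.2 cuts at rescue unless otherwise specified. Read with 12.2.2, a rescued subject may contribute a Week 24 weight, whereas a discontinued one contributes an earlier weight carried forward. Site interpretation can therefore change the data.
- **Operation of the 6.4.9.1 rule.** Its only trigger is a home reading, and no home-testing frequency is set for the period in which the 240 mg/dL limit applies.

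**Working it through.** The protocol gives no figure for this point, so the check compares thresholds, periods and triggers.

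**1. The two rules side by side**

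| | 6.4.9.1 | 3.1.4.1 / Table 1 |
|---|---|---|
| Period | Week 4 to 24 (240 mg/dL limit) | Week 12 to 24 |
| Starting trigger | two same-day home readings | central FPG at a visit |
| Confirmation | a similar central value | second central value on another day |
| Limit | above 240 mg/dL | above 200 mg/dL, no upper bound |
| Consequence | discontinue | can remain and can receive rescue |

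The periods overlap from Week 12 to Week 24, which is 12 of the 24 treatment weeks.

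**2. Values in the overlap**

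| FPG (mg/dL) | Above the 200 limit | Above the 240 limit |
|---|---|---|
| 210 | yes | no |
| 239 | yes | no |
| 241 | yes | yes |
| 270 | yes | yes |
| 300 | yes | yes |

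Any value above 240 is also above 200. A subject whose home readings and central values are both above 240, with two consecutive central values, satisfies both rules.

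**3. Tie-breaker.** Neither section refers to the other. Section 5.8.1 lists no FPG threshold. Section 6.3.1 (as revised by Amendment No 1) sets only when FPG is reported to the investigator: above 270 mg/dL in Weeks 0-4, above 240 in Weeks 4-12 and above 200 in Weeks 12-24. It attaches no action. So no tier or precedence is stated.

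**4. Home testing.** After randomisation a frequency is stated for Weeks 0-4, which is 4/24 = 17% of treatment weeks. The 240 mg/dL rule covers Weeks 4-24, which is 20 weeks, none with a stated frequency. Central FPG is measured at every visit (Tables 2 and 6). Between randomisation and Week 12, however, no FPG-specific action follows from a high central value alone: Table 1 has not opened, and 6.4.9.1 starts only from home readings.

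**5. Rescue by Week 12.** Visit 10 is Day 12 × 7 = 84, ± 3 days, so Day 81 to 87. The recheck is at least one day later.

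- Visit 10 on Day 84-87: earliest recheck Day 85-88, so no rescue by Day 84.
- Visit 10 on Day 81-83: earliest recheck Day 82-84, so rescue by Day 84 is possible only with very fast laboratory turnaround.
- No rescue under Table 1 can have begun by Visit 10 itself.

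The rescue part of the Week 12 composite is therefore near zero by design.

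**6. Sample size.** With n = 2·SD²·(z₁ + z₂)²/difference², SD 0.9, difference 0.5, two-sided level 0.027 (z₁ about 2.2115) and 90% power (z₂ about 1.2816): 2 × 0.81 × 3.4931² / 0.25 = 79.07, so 80. Then 80/0.95 = 84.2, so 85 per group and 3 × 85 = 255. The protocol's figures reproduce, and this point does not touch them.

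**The case against.** **The triggers differ and rescue is optional.** 6.4.9.1 starts from home readings; Table 1 needs two central values. A subject whose high values appear only at scheduled visits meets Table 1 alone. Because 3.1.4.1 is permissive, a site that discontinues breaches neither section. This narrows the conflict but does not remove it: a site that rescues a subject who meets both follows 3.1.4.1 and departs from 6.4.9.1. A tiered reading (rescue from 200 to 240, discontinuation above) is possible, but the protocol does not state it.

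**Glucose is still monitored.** A reader might infer that the hyperglycaemia safety net has no scheduled measurement after Week 4. The documents do not support that. Central FPG is taken at every visit and high values are reported to the investigator. Meters and diaries continue to Visit 13 in Table 2, and 6.4.9 has readings reviewed at each visit. What is missing is a home-testing frequency, which matters because home readings are the rule's only trigger.

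**5.8.1 is not silent on poor control.** Items 2 and 6 (risk, and a laboratory abnormality, as judged) and item 7 can cover it. It is right only that no FPG threshold is listed.

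**The analyses are largely insulated.** Glycaemic values after rescue are excluded and discontinued subjects are carried forward, so glycaemic data are truncated under either rule. The composite at Weeks 16 and 24 counts the subject either way, provided a 6.4.9.1 discontinuation is coded as lack of efficacy. This stands, and it limits the consequence to retention, safety exposure and non-glycaemic endpoints.

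**Insulin.** A reader might see item 7 of 5.8.1 as contradicting 5.6, where "Insulin use is permitted in the following cases". The ordinary reading is that the specific, time-limited permission qualifies the general rule. Only a cross-reference is missing.

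**Conclusion.** The conflict is real for subjects who, in Weeks 12-24, have two same-day home readings above 240 mg/dL with a similar central value and also two consecutive central values above 200 mg/dL. For them 6.4.9.1 directs discontinuation while 3.1.4.1 allows continuation with rescue, and the protocol does not resolve it. The mismatch between the period of the 6.4.9.1 rule and its home-testing schedule is also real.

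Two stronger readings are not supported. One is that every subject with confirmed FPG above 240 mg/dL is affected; the different triggers rule that out. The other is that the Week 12 comparison cannot count rescues and so cannot meet its objective. The outcome is a composite that still counts discontinuations, and an early Visit 10 leaves a small opening for rescue. The rescue part is near zero, not impossible, and the exact Week 12 cut-off may be set in the analysis plan, which was not available.

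The number of subjects affected, and its split between arms, cannot be derived from the protocol. The sample size is unaffected and the glycaemic carried-forward analyses largely so. The text is wrong as written and should be corrected, because two sites could treat the same subject differently and each cite the protocol.

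**What to change.** - Reconcile 3.1.4.1/Table 1, 5.8.1 and 6.4.9.1 so that each treatment period has one stated trigger and one stated consequence, including for a subject already on rescue. Which rule applies is for the clinical team to decide.
- Align the self-monitoring schedule in 6.4.9.1 with the period its rule covers, and state what follows, if anything, from a high central value alone before Week 12.
- Secondary: describe the Week 12 result of the composite in 12.2.2.3 as essentially discontinuation for lack of efficacy, and state that a discontinuation under the glucose rule is coded as such.
- Secondary: add to item 7 of 5.8.1 a cross-reference to the insulin allowance in 5.6.

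The cost is amendment wording and a notice to sites. If the clinical team extends scheduled home testing, subjects carry some extra testing. Sample size and the primary analysis do not change.

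### For FPG above 240 mg/dL in Weeks 12 to 24 the protocol has both a stop rule and a rescue rule without upper bound, and does not say which takes precedence

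*Protocol*

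**What the plan says.** Three places in the protocol bear on high fasting plasma glucose (FPG) in the second half of treatment.

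- **Section 6.4.9.1 (self-monitoring).** If the home reading is "above 240 mg/dL (13.2 mmol/L) from Week 4 (Visit 8) to Week 24 (Visit 13), the subject should repeat the FPG on the same day". When the repeat reading also exceeds the limit, "the subject should contact the study centre and be scheduled for a central laboratory FPG measurement within one week". Then: "If central laboratory values show similar values, the subject should be discontinued". The text makes no exception for rescue and does not change at Week 12.
- **Section 3.1.4.1 and Table 1 (rescue).** Between Visit 10 (Week 12) and Visit 13 (Week 24) the criterion is a central FPG above 200 mg/dL twice in a row. After a first high value at a visit, "the investigators should set up acting visit at some other day in order to recheck the FPG at central laboratory". The consequence is: "Subjects with inadequate glycemic control based on glycemic criteria as outlined in Table 1 can remain in the study and can receive rescue therapy". Table 1 gives no upper bound. Further on: "If glycemic control is not improved by the rescue therapy, the investigators can consider the discontinuation of the study", after consultation with the sponsor's study physician. Withdrawal is required only where neither rescue drug is suitable.
- **Section 5.8.1 (discontinuation criteria 1 to 14).** No criterion is based on FPG. Criterion 7, on the use of other anti-diabetic agents, exempts rescue treatment.

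**The concern.** Every value above 240 mg/dL is also above 200 mg/dL. From Week 12 on, therefore, the stop rule lies wholly inside the glucose range of the rescue rule. One passage says the subject should be discontinued; the other says the subject can stay and be rescued. Neither refers to the other.

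What is at stake is disposition. Whether a subject stays on blinded treatment to Week 24 can depend on whether a home meter or a scheduled sample first showed the high value. Poor control is more likely on placebo, so any loss of follow-up from this source would probably fall unevenly across the arms.

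**Working it through.** There is no stated figure to reproduce. The check sets the passages side by side.

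**1. Where the rules overlap.** The rescue window is Weeks 12 to 24 and the stop window is Weeks 4 to 24, so both apply in Weeks 12 to 24. In Weeks 4 to 12 no rescue rule exists and there is no conflict.

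| Central FPG, Weeks 12–24 (mg/dL) | Table 1 (above 200) | 6.4.9.1 (above 240) |
|---|---|---|
| 190 | no | no |
| 210 | rescue possible | no |
| 239 | rescue possible | no, unless it counts as 'similar' |
| 241, 260, 300 | rescue possible | should be discontinued |

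**2. What each route requires.** The stop needs two home readings on one day and one central value within a week. Rescue needs two central values on different days, starting from a visit. Take a true level of 250 mg/dL. Found at a visit and confirmed at the recheck, the subject may be rescued and stay. Found twice by the meter and confirmed centrally, the subject should be discontinued. A subject with high meter readings and two central values above 240 mg/dL meets both rules at once.

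**3. Whether another section settles it.** Section 5.8.1 does not contain the stop. Section 6.3.1, also as revised in Amendment 1, lowers the central FPG reporting limit from 240 to 200 mg/dL at Week 12, in line with the rescue window; section 6.4.9.1 has no such step. For a subject already on rescue, section 3.1.4.1 leaves discontinuation to consideration after consultation, while section 6.4.9.1 says it should happen.

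**4. What a stopped subject loses.** The most exposure that can be lost is 24 − 12 = 12 weeks. Visits 11 (Week 16) and 12 (Week 20) may be skipped. Visit 13 procedures are not lost: section 5.8.2 and note b to Table 2 bring them forward to within 7 days of stopping, and Visit 14 follows three weeks after stopping.

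**5. What changes in the analysis.**
- HbA1c and FPG: a rescued subject contributes the last value on or before the first rescue dose, and a stopped subject a value from about the time of stopping. Both date from around the event.
- Body weight (key secondary): section 12.2.2 drops post-rescue values only for glycaemic endpoints, so a rescued subject contributes a Week 24 weight and a stopped subject an earlier one carried forward. Section 11.1.2 drops post-rescue values unless otherwise specified, without that limit. Under that rule the difference largely disappears.
- Rescue or lack-of-efficacy endpoint (section 12.2.2.3): rescue counts. The stop counts only if it is coded as lack of efficacy, and the protocol does not say how to code it.

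**6. Size.** The protocol gives no rate. Suppose, as an assumption only, that 3–8% of placebo and 0–2% of active subjects exceed 240 mg/dL in these weeks. With 85 per arm:
- placebo: 0.03 × 85 = 2.6 to 0.08 × 85 = 6.8, about 3 to 7 subjects;
- each active arm: 0 to 0.02 × 85 = 1.7, at most about 2 subjects.

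Under these rates the counts are ceilings, because only subjects who reach the meter route face the stop. Section 6.4.9.1 states a self-monitoring frequency only up to Visit 8 (Week 4). Meters and diaries are nevertheless scheduled to Week 24 in Table 2, and the stop rule runs explicitly to Week 24.

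**The case against.** The strongest reply is that section 3.1.4.1 is permissive throughout: subjects can remain, can receive rescue, and discontinuation can be considered. A site that discontinues under 6.4.9.1 breaches nothing there. The two sections could be read as a rescue option above 200 mg/dL with a separate stop at a higher level. The two routes also require different evidence, so different outcomes are not purely an accident of detection. And the limit behind 'similar' can be guessed from the preceding sentence.

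Much of this stands, and it rules out several stronger readings that a reader might infer:

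- *That sites cannot comply with both sections.* Not supported, because discontinuing is compatible with permissive wording.
- *That stopped subjects supply no further data.* Not supported. Visit 13 procedures and Visit 14 are still required.
- *That the rescue or lack-of-efficacy endpoint is necessarily distorted.* Not supported. It pools both dispositions by design, and only the coding is open.
- *That non-glycaemic results are necessarily affected.* This holds under section 12.2.2 but not under section 11.1.2.

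What the reply does not remove is the gap itself. The protocol nowhere states that the higher level overrides rescue. A site that uses the rescue option for a subject who also meets the meter route departs from 6.4.9.1, and a site that consults 5.8.1 finds no such stop. Whether a central 235 mg/dL after meter readings of 245 mg/dL is 'similar' is left to each site. A statistical analysis plan could settle which weight values are used, but not an instruction to sites on who stays in the study.

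**Conclusion.** The point holds as an unreconciled pair of disposition rules. In Weeks 12 to 24, subjects with the same confirmed central FPG above 240 mg/dL can be treated differently according to detection route, and this extends to subjects already on rescue.

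The impact is modest. The primary HbA1c estimate is little affected. The loss per stopped subject is at most 12 weeks of blinded exposure and two intermediate visits. Effects on body weight and on the rescue or lack-of-efficacy endpoint depend on which data rule applies and on coding. The number affected is unknown and probably small; the counts above rest entirely on assumed rates, whereas the conflict rests on the text alone. It is worth correcting because it decides who remains on blinded treatment and costs almost nothing to put right. No view is taken on which rule is clinically right.

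**What to change.** Reconcile sections 6.4.9.1, 3.1.4.1 with Table 1, and 5.8.1, with cross-references, so that:

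- precedence is explicit, and one centrally confirmed FPG level in Weeks 12 to 24 leads to one disposition whether the meter or a visit sample found it;
- the disposition of subjects already on rescue is stated;
- the central-laboratory limit meant by 'similar' is given as a number;
- the discontinuation reason to be recorded for such a stop is named, so that its place in the rescue or lack-of-efficacy endpoint is fixed.

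The clinical content is for the sponsor to decide. The cost is protocol wording, with no extra visit, sample or subject.
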